### **10.3 HANDLING OF INCONSISTENCIES IN DATA AND OUTLIERS**

For lab values, distribution of each variable will be assessed. The extreme outliers will be treated as missing values, approaches to handling missing values are described in the previous section.

## **11. DATA ANALYSIS**

Please check section 9.7 of the study protocol

### **11.1 MAIN ANALYSIS**

During the first step of the comparative analysis, the baseline characteristics of the individual NOAC groups will be balanced with the warfarin group to account for potential confounding effects through an inverse probability of treatment weighting (IPTW) method. A multinomial logistic regression model will be used to estimate the generalized propensity score (GPS). The treatment membership (warfarin, dabigatran and rivaroxaban) is the dependent variable and all the covariate variables listed in [Annex 4](#) except for “Anti-platelet drugs” and “The number of anti-platelet drugs per prescription” are independent variables in the multinomial logistic regression model, as the two variables can be fully derived from the variable “Anti-platelet use duration”. For each patient, we will obtain the estimated GPS vector with components of the probabilities of receiving each treatment (warfarin, dabigatran and rivaroxaban) through the multinomial logistic regression model.

The stabilized IPTW (s-IPTW) will be used to deal with the inflation of type I error and extremely large weight when using regular IPTW. The s-IPTW is calculated as

$$w_i = \frac{\Pr(T = k)}{\Pr(T = k|X = x_i)}$$

for the  $i$ th patient, where  $T$  is the treatment membership and  $x_i$  is the covariates of this patient. The denominator is the  $k$ th component of GPS vector of the  $i$ th patient who was actually in treatment group  $k$  and the numerator is the marginal probability of receiving treatment  $k$  [\[R22-1420\]](#).

The GPS distributions (density curves, boxplots) of each treatment will be used to examine GPS overlap between the treatment groups. Patients outside of the common support or overlap area for any component of the GPS vector are removed from the analysis. The area of common support is formed by defining boundaries for each component  $k$ ,  $k = 1, 2, 3$  of the GPS vector [\[R22-1419\]](#):

$$\Pr(T = k|x)^{low} = \max[\min(\Pr(T = k|x, T = 1)), \min(\Pr(T = k|x, T = 2)), \min(\Pr(T = k|x, T = 3))]$$

$$\Pr(T = k|x)^{high} = \min[\max(\Pr(T = k|x, T = 1)), \max(\Pr(T = k|x, T = 2)), \max(\Pr(T = k|x, T = 3))]$$

[figure not shown]
The distributions of s-IPTW for each treatment group will be examined, the mean s-IPTW is expected to be close to 1. Weight truncation based on the distributions of s-IPTW will be applied if there are extremely high s-IPTW.

Proprietary confidential information © 2022 Boehringer Ingelheim International GmbH or one or more of its affiliated companies

The baseline demographics, risk factors, and clinical characteristics will be compared between the treatment groups (dabigatran vs warfarin, rivaroxaban vs warfarin, dabigatran vs rivaroxaban) using the absolute standardized difference (ASD) pre- and post- s-IPTW to assess the balance of these confounders. A covariate will be considered well balanced if the ASD is below 0.1.

A Cox proportional hazard regression model with s-IPTW will be used to estimate adjusted hazard ratios (aHRs) of treatments (dabigatran vs warfarin, rivaroxaban vs warfarin) and their 95% CIs on primary, secondary, and further outcomes. The treatment membership is the independent variable in the model. A patient will be censored if discontinuation of the index OAC or switching to another OAC or death or loss to follow-up occurred before outcome event. If substantial covariate imbalance between treatment group is noted assessed by a standardized difference  $>0.1$ , then the Cox proportional hazard model will be further adjusted by including covariates that are out of balance in the model. A robust sandwich variance estimation of the treatment effect estimates will be used to account for the fact that the pseudo-population size is inflated or deflated relative to the original population and that weights are estimated [\[P21-02302\]](#).

A sensitivity analysis will be performed by restricting the follow-up period to 3 years for Cox regression models on primary and secondary outcomes.

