## 7. RATIONALE AND BACKGROUND

Atrial fibrillation (AF) is a common cardiac arrhythmia and is associated with 15-20% of all strokes [R96-0267], [R96-0252]. Among AF patients, the prevalence of concomitant coronary artery disease (CAD) is estimated to range from 17% to 46.5% [P17-09543], which can increase the risks of major bleeding, stroke, and mortality [R21-3491]. The management of AF is complicated by the presence of concomitant CAD when co-prescription of oral anticoagulation (OAC) with antiplatelet therapy is needed. Therefore, careful considerations are necessary in choosing antithrombotic therapies to balance the bleeding risk, stroke risk, and other thrombosis risks.

Non-valvular atrial fibrillation (NVAF) is a subtype of AF. The 2020 European Society of Cardiology (ESC) Guidelines recommends non-vitamin K oral anticoagulant (NOAC) treatments over warfarin for eligible oral anticoagulant-naïve NVAF patients [P21-09613]. Dabigatran and rivaroxaban are the first two NOACs approved for thromboprophylaxis of AF, which are also the two widely used NOACs in Asia. According to RE-LY and ROCKET-AF, both dabigatran and rivaroxaban have shown at least equal efficacy compared to warfarin in the prevention of stroke/systemic embolism (SE), and dabigatran 110 mg bid demonstrates superiority over warfarin in major bleeding among NVAF patients [P09-11669], [R11-4223]. Further, post hoc or subgroup analyses of the two pivotal trials indicate consistent superiority in the safety profiles of NOACs versus warfarin among NVAF patients with concomitant CAD [P12-00109]. However, the current literature lacks comparative assessment of clinical outcomes among Asian NVAF patients with CAD who are managed with warfarin, dabigatran, or rivaroxaban in routine clinical practice. Given the increased risks of major bleeding and recurrent coronary events associated with CAD, it is necessary to evaluate the safety outcomes and net clinical benefits among Asian NVAF patients with concomitant CAD.

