### **9.7.1 Main analysis**

Comparative analysis for primary and secondary outcomes will be conducted between treatment groups. The comparative analysis will follow a two-step approach. The first step will compare the baseline characteristics and clinical outcomes of individual NOAC (Dabigatran, Rivaroxaban) -versus warfarin-treated groups.

[figure not shown]
During the first step of the comparative analysis, the baseline characteristics of the individual NOAC groups will be balanced with the warfarin group to account for potential confounding effects. Propensity scores will be calculated based on multinomial logistic regressions, with all covariates being incorporated. Next, an inverse probability of treatment weighting (IPTW) method will be applied using the calculated propensity score to avoid sample size inflation and to ensure appropriate estimation of variances. Yet, the IPTW estimates can be heavily influenced by large weights, thus destabilizing the results. To increase the robustness of the model, weight truncation will be applied once the distribution of propensity score is available. The distribution of propensity scores will be described, based on which the cut-off points of weight estimates will be chosen. Lastly, the calculated stabilized IPTW (s-IPTW) estimates will be applied to obtain two comparative pairs of individual NOAC vs. warfarin groups, for which the baseline demographics, risk factors, and clinical characteristics will be compared

using the absolute standardized difference (ASD) pre- and post- IPTW to assess the balance and model robustness. A covariate (baseline demographics, risk factors, clinical characteristics) will be considered well balanced if the ASD is below 0.1.

A Cox proportional hazard regression model with the time since NOAC drug index date as the underlying timescale will be used to compute adjusted hazard ratios (aHRs) with 95% CIs. If substantial covariate imbalance between treatment group is noted assessed by a standardized difference  $>0.1$ , then outcome models will be further adjusted by covariates that are out of balance using multivariable Cox proportional hazards models.

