### **7.2 SETTING**

**Study Period:** the entire time period that includes the look-back period, the cohort entry date (drug index date), and follow-up period for the study population. The study period will be from April 18th, 2011 (start of data collection) to December 31st, 2020 (end of data collection).

**Patient Selection Period:** the time period for which patients are eligible to enter the cohort, which is from April 18th, 2012 to December 31st, 2020.

**Cohort Entry Date:** The drug index date, defined as the first date of prescription for dabigatran, rivaroxaban, or warfarin during the patient selection period.

**Look-back Period:** the 365-day period that ends 1 day prior to the cohort entry date. The earliest start date of the look-back period is April 18th, 2011.

**Loss of follow-up:** the last data point available in the database during the study period.

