#### ANNEX 4. STUDY COVARIATES

N	Category	Variables	Definition
1	Demographic characteristics	Age	- By year (calculated on index date)
		Gender	- Male, Female
2	Ischemic and hematologic characteristics	CHA2DS2-VASc score	Codes used to define elements of CHA2DS2-VASc score in the following excel file:   11600308 CHA2DS2_VASc.xlsx
		HAS-BLED score	Codes used to define elements of HAS- BLED score in the following excel file:   1160-0308 HASBLED.xlsx
3	Comorbidities	Heart failure	ICD-10 diagnosis codes presented in the following excel file:
		Peripheral arterial disorder	
		Hypertension	
		Diabetes	

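### Calendar year of anticoagulant start is missing from the propensity model, the visible balance table and the Cox model, so era can confound each NOAC versus warfarin comparison unseen

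*SAP*

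**What the plan says.** - **Entry window.** SAP section 7.2 sets the patient selection period, "which is from April 18th, 2012 to December 31st, 2020". Protocol section 9.2 gives the same dates.
- **Propensity model.** SAP section 11.1 uses "all the covariate variables listed in" Annex 4, minus two antiplatelet variables that can be derived from a third. Protocol section 9.7.1 agrees: "Propensity scores will be calculated based on multinomial logistic regressions, with all covariates being incorporated".
- **Covariate list.** Annex 4 and protocol section 9.3.3 cover age, gender, two risk scores, comorbidities, co-medications and procedures. Neither has an index year, index date or entry period. The one entry that mentions a year, "By year (calculated on index date", defines age.
- **Outcome model.** SAP section 11.1: "The treatment membership is the independent variable in the model". Covariates join it only if their standardized difference exceeds 0.1. The time axis is "time since NOAC drug index date as the underlying timescale" (protocol section 9.7.1), so calendar time does not enter there either.
- **Balance table.** Table 2a, in protocol Annex 3 and SAP Annex 5, has no calendar row.
- **Nearest provisions.** These are a sensitivity analysis "restricting the follow-up period to 3 years for Cox regression models on primary and secondary outcomes" (SAP section 11.1) and 1:1 propensity score matching (protocol abstract), for which no year variable is named. The ENCePP checklist, item 10.4, answers No on stratified analyses. Protocol section 9.9 does not mention calendar time as a limitation.

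**The concern.** A variable confounds if it is related both to treatment and to outcome after adjustment for what is in the model. Year of start is a natural candidate in a new-user cohort that recruits over almost nine years. The share of starters on each drug may move, and so may the recorded bleeding rate, because major bleeding is built from diagnosis codes and hospital claim types (SAP section 8.2.1 and Annex 3).

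The plan's safeguard is conditional. The Cox model is extended only for covariates seen to be out of balance, and year is not tabulated. A large imbalance in entry year could sit behind a balance table in which every listed row is below 0.1. The weighted HR would then carry the era difference, with a narrow confidence interval because the cohorts are large.

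**Working it through.** **Inputs from the documents.** Entry from 18 April 2012 to 31 December 2020; about 17000 warfarin, 11000 rivaroxaban and 4000 dabigatran starters; 3 events per 100 patient-years; 1 year of exposure; HR 0.66 and 0.74; 20% sample loss (protocol section 9.5). Two-sided alpha of 0.05 is assumed from the 95% CIs.

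**The plan's own figure.** Schoenfeld events for HR 0.66 at 80% power and 1:1 allocation: 4 × (1.960 + 0.842)² / (ln 0.66)² = 182. Then 182/0.03 = 6067, against 6050 stated, and 182/0.045 = 4044, against 4040 stated. With 20% loss, 3025/0.8 = 3781, as stated. The concern does not rest on these figures; they only set the scale.

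**Length of the window.** It spans 3179 days, or 8.7 years. Potential follow-up therefore runs from 8.7 years down to zero. Anyone entering after 31 December 2017 cannot reach 3 years, so the 3-year restriction weakens the link between entry year and follow-up but does not remove it.

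**Illustrative bias.** The documents give no index-year distribution and no bleeding trend, so both inputs here are assumptions. Let g be the yearly change in bleeding hazard that the listed covariates do not explain, and d the difference in mean entry year that remains between the arms. With a log-linear trend and entry distributions of similar shape, the HR is multiplied or divided by (1 + g)^d:

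| g per year | d = 1 | d = 2 | d = 3 |
|---|---|---|---|
| 2% | 1.02 | 1.04 | 1.06 |
| 5% | 1.05 | 1.10 | 1.16 |
| 10% | 1.10 | 1.21 | 1.33 |

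At g = 5% and d = 2 the factor is 1.05² = 1.1025:
- true 0.66 reads as 0.66/1.1025 = 0.60 or 0.66 × 1.1025 = 0.73;
- true 0.74 reads as 0.67 or 0.82.

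**Effect on error rate if the true HR is 1.** Take the database counts less 20%, 3 events per 100 patient-years and 1 year, and ignore weighting variance.
- Warfarin: 17000 × 0.8 × 0.03 = 408 events.
- Dabigatran: 4000 × 0.8 × 0.03 = 96 events; SE = √(1/96 + 1/408) = 0.113.
- Rivaroxaban: 11000 × 0.8 × 0.03 = 264 events; SE = √(1/264 + 1/408) = 0.079.

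With ln 1.1025 = 0.098, the two-sided error Φ(−1.96 + 0.098/SE) + Φ(−1.96 − 0.098/SE) is about 14% for dabigatran and 24% for rivaroxaban, instead of 5%. At g = 2% and d = 1 it is 5.3% and 5.7%, which is negligible.

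**The case against.** Much of the opposing case stands, and it limits what can be claimed.

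**No trend is documented.** A reader might infer that the comparison is confounded by era. The documents support only that it can be. The background says "The 2020 European Society of Cardiology (ESC) Guidelines recommends non-vitamin K oral anticoagulant (NOAC) treatments over warfarin" for eligible patients. That is one European guideline dated in the last year of the window. It shows neither a shift across 2012-2020 nor Japanese practice. Changes in coding over time, or in the hospitals contributing data, are plausible but not described.

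**Direction is open.** A reader might also infer that the bias favours the NOACs. Suppose 70% of warfarin and 35% of NOAC starts fall in the early half of the window, with an early/late bleeding-rate ratio of 1.3. The factor is (0.35 × 1.3 + 0.65)/(0.70 × 1.3 + 0.30) = 1.105/1.21 = 0.91. Invert the rate ratio and the factor is 0.919/0.838 = 1.10. The sign comes from the assumption.

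**Co-therapy is partly handled.** Antiplatelet duration by number of agents, proton pump inhibitors, gastric secretion inhibitors, NSAIDs, statins and coronary revascularisation are in Annex 4 and so in the score. Only trends beyond these baseline variables remain.

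**Follow-up length is not a confounder in itself.** A Cox model on time since start accommodates unequal administrative censoring. Follow-up also ends at discontinuation or switching, and protocol section 9.5 cites mean treatment durations of 265 to 868 days, so the 2020 cut-off is not the only limit. What remains is that censoring depends on entry year, which the model does not condition on. That is a consequence of the same omission, not a second fault.

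**Some text is hidden.** Protocol section 9.7.2 and SAP section 11.2 are redacted, and the full table shells are in an attachment. It cannot be said that no period analysis exists. The primary score, its covariate list and the Cox model are visible, and year is in none of them.

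**Conclusion.** The omission is established for the visible primary analysis: index year is not in Annex 4, the propensity score, the displayed balance table or the Cox model, and the balance-triggered adjustment cannot detect what is not tabulated. Whether it biases the result is unknown from the documents. It does so only if drug choice and recorded bleeding both moved with calendar time beyond the listed covariates. Under the assumed ranges (2-10% per year, 1-3 years' difference in mean entry) the HR is off by a factor of 1.02 to 1.33 in either direction. The low end is harmless. The high end would nearly erase a true 0.74 (0.74 × 1.33 = 0.98) or exaggerate it (0.74/1.33 = 0.56). These are illustrations, not expected bias. The change should be made because it closes a visible gap cheaply; the documents do not show that the planned estimate is wrong.

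**What to change.** 1. Add index year, categorical or in two-year bands, to Annex 4. It then enters the multinomial score under the existing wording. Put it in the matching score and in the balance table before and after weighting.
2. Report the distribution of entry year by arm. If the arms do not differ, the question is closed.
3. After weighting, check balance on year itself. The common-support rule in SAP section 11.1 bounds the components of the score. It does not guarantee overlap within each year, and truncation can leave year imbalance behind.
4. Report the effective sample size, (Σw)²/Σw², per arm.

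The variable costs nothing to obtain, because the index date is already derived for every patient (SAP section 8.1). The real cost is more variable weights, and possibly more trimming or truncation, if a drug is rare in some years. That matters most for dabigatran. About 4000 patients are available against 3781 required, and a loss above 1 − 3025/4000 = 24% would take the arm below the plan's own 3025. Two-year bands keep this cost lower than single years, with coarser control of era.

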**11.3 SAFETY ANALYSIS**

Please check section 9.7.3 of the study protocol

**12. QUALITY CONTROL**

Please check section 9.8 of the study protocol

**ANNEX 1. LIST OF [REDACTED] RECEIPT CODE FOR OAC**

OAC	Receipt Code	Description
Warfarin	610450012	Warfarin K Tablets 1mg [B01A0]
	610460002	Arefarin Tablets 1mg [B01A0]
	610462024	Warfarin Potassium Tablets 0.5mg (HD) [B01A0]
	610462025	Warfarin Potassium Tablets 2mg (HD) [B01A0]
	610463227	Warfarin Potassium Tablets 0.5mg [B01A0]
	610463228	Warfarin Potassium Tablets 2mg [B01A0]
	613330001	Warfarin Potassium Tablets 1mg [B01A0]
	613330002	Warfarin Potassium Tablets 5mg [B01A0]
	613330003	Warfarin Tablets 1mg [B01A0]
	613330004	Warfarin Tablets 5mg [B01A0]
	620000731	Warfarin Potassium Tablets 1mg (HD) [B01A0]
	620002332	Warfarin Tablets 0.5mg [B01A0]
	620002472	Warlin Tablets 0.5mg [B01A0]
	620002473	Warlin Tablets 1mg [B01A0]
	620811502	Warfarin K Tablets 1mg (F) [B01A0]
	620811503	Warfarin K Tablets 1mg (NISSIN) [B01A0]

Proprietary confidential information © 2022 Boehringer Ingelheim International GmbH or one or more of its affiliated companies

	620811507	Warfarin K Tablets 1mg (TEVA) [B01A0]
	620811510	Warfarin K Tablets 1mg (TOWA) [B01A0]
	620811511	Warfarin K Tablets 1mg (NP) [B01A0]
	621480504	Warfarin K Tablets 0.5mg (TEVA) [B01A0]
	621480506	Warfarin K Tablets 0.5mg (TOWA) [B01A0]
	621480507	Warfarin K Tablets 0.5mg (NP) [B01A0]
	621480604	Warfarin K Tablets 2mg (NP) [B01A0]
	621938101	Warfarin K Fine Granules 0.2% (NS) [B01A0]
	621940901	Warfarin K Fine Granules 0.2% (YD) [B01A0]
	622122601	Warfarin Granules 0.2% [B01A0]
Dabigatran	622043301	Prazaxa Capsules 75mg [B01E0]
	622043401	Prazaxa Capsules 110mg [B01E0]
Rivaroxaban	622068301	Xarelto Tablets 10mg [B01F0]
	622068401	Xarelto Tablets 15mg [B01F0]
	622449101	Xarelto Fine Granules Packet 10mg [B01F0]
	622449201	Xarelto Fine Granules Packet 15mg [B01F0]
	622829001	Xarelto OD Tablets 10mg [B01F0]
	622829101	Xarelto OD Tablets 15mg [B01F0]
Apixaban	622224901	Eliquis Tablets 2.5mg [B01F0]
	622225001	Eliquis Tablets 5mg [B01F0]
Edoxaban	622080901	Lixiana Tablets 15mg [B01F0]
	622576001	Lixiana OD Tablets 15mg [B01F0]
	622081001	Lixiana Tablets 30mg [B01F0]
	622576101	Lixiana OD Tablets 30mg [B01F0]
	622375201	Lixiana Tablets 60mg [B01F0]
	622576201	Lixiana OD Tablets 60mg [B01F0]

## ANNEX 2. CODE USED TO CREATE STUDY POPULATION

DIGNOSIS CODE:

Indication	ICD-10/ disease code	Description
AF	I48	Atrial fibrillation and flutter
	I48.0	Paroxysmal atrial fibrillation
	I48.1	Persistent atrial fibrillation
	I48.2	Chronic atrial fibrillation
	I48.3	Typical atrial flutter
	I48.4	Atypical atrial flutter
	I48.9	Atrial fibrillation and atrial flutter, unspecified
VAF	8846941	valvular atrial fibrillation

Proprietary confidential information © 2022 Boehringer Ingelheim International GmbH or one or more of its affiliated companies

CAD	4140014	coronary artery disease
	8831577	coronary artery heart disease
	I20	Angina pectoris
	I20.0	Unstable angina
	I20.1	Angina pectoris with documented spasm
	I20.8	Other forms of angina pectoris
	I20.9	Angina pectoris, unspecified
	I21	Acute myocardial infarction
	I21.0	Acute transmural myocardial infarction of anterior wall
	I21.1	Acute transmural myocardial infarction of inferior wall
	I21.2	Acute transmural myocardial infarction of other sites
	I21.3	Acute transmural myocardial infarction of unspecified site
	I21.4	Acute subendocardial myocardial infarction
	I21.9	Acute myocardial infarction, unspecified
	I22	Subsequent myocardial infarction
	I22.0	Subsequent myocardial infarction of anterior wall
	I22.1	Subsequent myocardial infarction of inferior wall
	I22.8	Subsequent myocardial infarction of other sites
	I22.9	Subsequent myocardial infarction of unspecified site
	I23	Certain current complications following acute myocardial infarction
	I23.0	Haemopericardium as current complication following acute myocardial infarction
	I23.1	Atrial septal defect as current complication following acute myocardial infarction
	I23.2	Ventricular septal defect as current complication following acute myocardial infarction
	I23.3	Rupture of cardiac wall without haemopericardium as current complication following acute myocardial infarction
	I23.4	Rupture of chordae tendineae as current complication following acute myocardial infarction
	I23.5	Rupture of papillary muscle as current complication following acute myocardial infarction
	I23.6	Thrombosis of atrium, auricular appendage, and ventricle as current complications following acute myocardial infarction
	I23.8	Other current complications following acute myocardial infarction
	I24	Other acute ischaemic heart diseases
	I24.0	Coronary thrombosis not resulting in myocardial infarction
	I24.1	Dressler syndrome
	I24.8	Other forms of acute ischaemic heart disease
	I24.9	Acute ischaemic heart disease, unspecified
	I25	Chronic ischaemic heart disease

# BOEHRINGER INGELHEIM Group of Companies

## Statistical and Epidemiological Analysis Plan (SEAP) for Non-Interventional Studies (NIS)

c38948754-01

Page 20 of 32

Proprietary confidential information © 2022 Boehringer Ingelheim International GmbH or one or more of its affiliated companies

	T82.9	Unspecified complication of cardiac and vascular prosthetic device, implant and graft
Rheumatic heart disease	I09	Other rheumatic heart diseases
	I09.0	Rheumatic myocarditis
	I09.1	Rheumatic diseases of endocardium, valve unspecified
	I09.2	Chronic rheumatic pericarditis
	I09.8	Other specified rheumatic heart diseases
	I09.9	Rheumatic heart disease, unspecified
Venous thromboembolism	I26	Pulmonary embolism
	I26.0	Pulmonary embolism with mention of acute cor pulmonale
	I26.9	Pulmonary embolism without mention of acute cor pulmonale
	I80.2	Phlebitis and thrombophlebitis of other deep vessels of lower extremities
Pregnancy	codes presented in the following excel file:   1160-0308 diagnosis_pregnancy.xls	

